#### Risks of Magnetic Resonance Imaging (MRI)

Because radiation is not used, there is no risk of exposure to radiation during an MRI procedure. However, due to the use of the strong magnet, MRI cannot be performed on patients with internal metallic objects such as implanted pacemakers, intracranial aneurysm clips certain prosthetic devices. Patients will be asked if they have any type implants. Patients with implants may undergo a CT scan without contrast. Also, subjects may feel nervous about tight spaces.

#### Adequacy of Protection Against Risks

Recruitment and informed consent: The Digital Detection of Dementia (D) studies will be approved by the Indiana University-Purdue University at Indianapolis Institutional Review Board. Indiana University-Purdue University (IUPUI) at Indianapolis Institutional Review Board will be the single IRB for this trial. University of Miami will submit a request for a reliance agreement. Trained research assistants will work with the practice managers from each primary care practice to identify potential subjects who meet the inclusion and exclusion criteria for the Clinical Validation study. Recruitment will be performed over the telephone, Zoom, or in-person at primary care practices for those eligible to participate in the clinical validation study, following HIPAA compliant standard recruitment procedures. The research assistants will make initial contact via telephone, Zoom or face to face at the primary care practices to garner interest in participating in the study and verifying the patients' eligibility. Our studies will require two written informed consent forms. The first one, for the clinical validation study will be completed per eligible participant and countersigned by the researcher and the second one, is consent from the practice leadership, after receiving an informed consent waiver from the IRB for patients receiving care in all of practices enrolled in the pragmatic trials. The informed consent process will be completed prior to conducting any baseline assessments.

Blood Draws and MRI Protections: Blood draw risks will be minimized by blood being drawn by experienced staff members. For MRI, If subjects feel uncomfortable due to the tightness of the space, we can pause and try the MRI again.

Protection against risk: Patients who refuse to participate in the Clinical Validation study will not be approached again. The patient's medical record will only be reviewed after obtaining informed consent from the participants in the clinical validation study (Stage III) and from the practice leadership (after receiving an informed consent waiver from the IRB), for patients

receiving care in all of practices enrolled in the pragmatic trials (Phase IV). To avoid the risk of inadvertent disclosure of PHI, all study personnel will be educated about general principles of subject access, informed consent, confidentiality, data safeguarding, and privacy requirements, and will complete an on-line course required by the Indiana University Purdue University Institutional Review Board. The format and the procedure of data collection will be outlined in the consent form, the data will be extracted into a pre-designed database, and the research assistant will not collect any additional data without the consent of the patient and approval by university IRB. Each study participant will be assigned a study identification (ID) number, and this ID number will be used rather than names and medical record numbers on all PHI data collected.

The principal investigators will disclose the finding of new information about the patient's health status directly to the patient and if the participant agrees, to the primary care physician. The principal investigators will be available to clarify any questions and offer any needed consultation. Efforts will be made to keep patients' personal information confidential. In addition, the investigators are planning to have continuous feedback from the patient and the practice staff to discuss any problems encountered during the data collection.

Reporting unanticipated problems involving risk to participants: A data safety monitoring board (**DSMB**) will be established, and will include a primary care physician, Geriatrician, patient representative, and biostatistician. The DSMB will meet prior to the first patient enrollment, to review the protocol for any major concerns prior to implementation. Subsequently, the DSMB will meet periodically to review and evaluate the accumulated study data for participant safety, study conduct and progress and scientific validity and integrity of the trial.

### **Potential Benefits of the Proposed Research to the Subjects and Others**

Although our studies are collecting data to test the accuracy and effectiveness of two scalable approaches for early detection of (ADRD) among older adults attending primary care practices, we anticipate some immediate benefit to participants. Detecting cognitive decline early and at low-cost is beneficial to patients and caregivers alike. The screening results will assure of the negative screening results, and those with positive screening results will receive a referral for appropriate diagnostic and management services. Early detection of ADRD will lead to early management of its cognitive, functional, and psychological disabilities, which if goes unmanaged, results in significant burden for patients, families, healthcare delivery systems and the entire society. In turn, early detection of ADRD could reduce such a burden, in addition to becoming increasingly important for assuring that people receive early ADRD disease modification treatment when available.

### **Importance of the Knowledge to be Gained**

Alzheimer's disease and related dementias (ADRD) negatively impact millions of Americans. Currently, half of Americans living with ADRD never receive a diagnosis. For those who do, the diagnosis often occurs two to five years after the onset of symptoms. The data may lead to national early detection and management program for ADRD as an efficient and beneficial method of reducing the current and future burden of ADRD. We are unaware of any similar studies that has been or will be conducted in a diverse primary care setting. Our studies will inform the scientific community and the health care system about the performance, including accuracy and effectiveness of the two scalable approaches in early detection of ADRD and improving the annual rate of new documented ADRD in primary care practices. Our studies will provide some knowledge about the specific characteristics of the primary care patients, and their attitudes toward early detection of ADRD and subsequent referral for appropriate diagnostic and management services. The knowledge gained will increase the power of care

delivery at our study sites by leveraging machine learning. This will make our health systems smarter and help to prevent avoidable hospitalizations and other negative ADRD outcomes.

ClinicalTrials.gov Registration: The Digital Detection of Dementia (D) studies will be registered at clinicaltrials.gov.

## F. DATA AND SAFETY MONITORING PLAN

The proposed pragmatic Clustered-comparative effectiveness trials are considered Quality Improvement project. However, we will construct a data safety monitoring plan (DSMP) for the trials and the clinical validation study. This DSMP will be monitored by the co-PIs and a three-member Data Safety and Monitoring Board (DSMB). The co-PIs will also conduct data and safety monitoring and will regularly monitor progress, goal achievement, and overall research direction in consultation with the co-investigators. In regard to the pragmatic trials, the team will use the Epic EHR system log to monitor the uptake and usage of the Annual Wellness visit with and without the deployed screening approaches of the Passive Digital Marker (PDM) and the Quick Dementia Rating Scale (QDRS) within the Epic computerized decision support (CDS). If uptake during the go-live period appears problematic, we will be able to revisit training and socializing the enhanced AWV with clinical staff or alter the user interface based on feedback.

### Data Monitoring and Reporting

The frequency of data review for these studies are summarized in the following tables:

Data Type: Clinical Validation Study	Frequency of Review		
	Each Occurrence	At assessment (Baseline)	End of study
Subject accrual (adherence to inclusion/exclusion); completion of the screening and the diagnostic assessment		X	
Protocol violations/noncompliance	X		
Out of range data		X	
Risk-benefit ratio assessment			X

Data Type: Pragmatic Trials– All data capture will be from the EHR	Quarterly	Annual
Adverse events, Unscheduled acute care utilization	X	X
Usage of the AWV with and without the PDM and the QDRS	X	X
Risk- Benefit ratio assessment		X

The project manager and the biostatistician will generate reports for each pragmatic trial that will contain:

- A) summary of all-source adverse events and an explanation of how each event was handled;
- B) the usage of the AWV with and without the PDM or the QDRS, and
- C) completion of the diagnostic assessment for those who screened positive;

All reports will be submitted to the Indiana University Purdue University of Indianapolis (IUPUI) IRB at time of continuing review.

Note: University of Miami will submit a request for a reliance agreement; IUPUI IRB will be the reviewing IRB for this study.

### Protection of data

Database security is maintained using a multi-layered approach to both limit access and the ability to alter data. There are strong protections restricting access to the researchers'

network. Local installation of proprietary software is required to detect our server on the network. Each authorized user has a unique username and password that allows specific access and editing privileges. Browsing level access only is used except when data entry/editing is explicitly intended. While multiple authorized users can simultaneously view data, only a single specifically authorized user can edit a given record at any time. The database is stored on a secure server, which is also password protected and only accessible to authorized lab personnel, in our locked laboratory offices. Database backups are conducted on a regular basis. Raw data, regardless of capture method, are accessible only to key research personnel; and all electronic information is stored on password-protected computers. The PIs will additionally regularly monitor the data collection and analysis process for data appropriateness, comprehensiveness, accuracy, and timeliness.

### **Safety Monitoring Definitions**

Adverse Event (AE) - Any untoward or unfavorable medical occurrence in a human subject, including any abnormal sign, symptom, or disease, temporally associated with the subject's participation in the research, whether or not considered related to the subject's participation in the research. We will use the EHR system to monitor the following AEs:

- Emergency room visits, not requiring hospitalization
- Breach of confidentiality
- Suicidal ideation not requiring intervention

Serious Adverse Event (SAE) is any adverse events that result in the following, which we will monitor:

- Death
- Persistent or significant disability/incapacity
- Inpatient hospitalization or prolongation of existing hospitalization
- Suicidal attempt or ideation requiring intervention

Study-Related – An AE or SAE is considered study related if the PI determines that the AE or SAE to be definitely, probably, or possibly related where possibly related means there is reasonable possibility that the incident, experience, or outcome may have been caused by the procedures or interventions involved in the research. AEs or SAEs judged as remotely related or not related are not considered study related.

Unanticipated Problem or Unexpected AE/SAE – problems or events in which the research places participants or others at a greater risk of harm (including physical, psychological, economic, or social harm) than was previously known or recognized. The term “unanticipated problem” is used in this context because some situations may not have produced an adverse event but is still considered an unanticipated problem (e.g. unsecured or stolen patient data which may not result in an AE). An event is unexpected if it is not described in the package insert of cessation medication, in the study protocol, or in the informed consent document.

### **Measurement and Reporting of Adverse Events**

Adverse event rates associated with screening interventions are low and are expected to vary little between the intervention and control groups in the two pragmatic trials. We will present blinded adverse event data to the co-PIs throughout the trials. We plan to present unblinded adverse events data to the DSMB panel when requested and at the annual meetings. If there is evidence of elevated adverse events, the PIs will consult with the

study team and use an adverse event form to report injuries or other adverse events caused by the intervention and detected through sources listed below.

### **Event Detection and Reporting**

No serious adverse events (SAEs) are expected for the two pragmatic trials. Our CHOICE trial found no negative impact of screening on depression, anxiety, quality of life, or health care utilization; thus, the only expected Adverse Events (AE) is loss of confidentiality. The Annual Wellness visit is the current standard of care.

All AEs reported by any of the primary care clinics or detected by the quarterly EHR review will be recorded and monitored. Each event will be documented on the basis of AE or SAE, severity, expectancy, and relatedness (definitely related, possibly related, or not related to study activities). The Principal Investigators (PIs) will be notified of all reportable events, including SAEs, within 24 hours. SAEs will be reported by telephone to the IUPUI IRB within 48 hours. A summary of SAEs will be included in annual IRB reporting. Annual Reports submitted to the IRB will contain the number of AEs and SAEs in the prior year and an explanation of how each event was handled. The annual IRB report will also contain the following: number of complaints and how each complaint was handled and the number of patient who did not complete the diagnostic assessment following screen positive results within the AWV.

SAEs that are unanticipated and definitely related to the intervention will be reported to the NIH Program Officer within 48 hours of the study's knowledge of the SAE.

### **SAE/AE Response and Reporting Procedure**

- 1) Research staff becomes aware of AE/SAE (via scheduled reviews of EHR data)
- 2) Research staff notifies [name] and/or [name] immediately if the event is an SAE or if immediate psychiatric or medical intervention is required, and within 7 days if the event is an AE.
- 3) [name] and/or [name] will conduct EHR review when necessary to gather additional information about the event.
- 4) [name] and/or [name] will report AE/SAE to DSMB to aid in determining:
  - a. Severity: Mild, Moderate, Severe
  - b. Expectedness: Expected, Unexpected
  - c. Study Related: Definitely, Probably, Possibly, Remotely, Note Study-Related
- 5) Project staff documents AE/SAE and DSMB determination in study database. The report will be provided to a NIA Program Officer.
- 6) [name] and/or [name] will prepare a report for the IRB as per local, state, and federal reporting requirements.
- 7) If a death occurs, [name] and/or [name] will report it to the DSMB and NIA Program Officer within 48 hours of knowing about the event.
- 8) DSMB will aid in planning measures to prevent future occurrences, if any warranted.
- 9) [name] and/or [name] will make changes to protocol and/or consent form if needed.

To enhance monitoring and study oversight, DSMB and study staff will meet once per 6 month.

### **Possible Adverse Events**

Adverse events will be monitored on an ongoing basis by the study manager from three sources:

1. Self-initiated phone, e-mail, or in-person report by the participant in the clinic validation study or by the primary care clinical team for the pragmatic trials.

2. Quarterly review of acute care utilization in the pragmatic trials.

The co-PIs will be notified within 24 hours of any adverse events. Serious adverse events will be reported within 5 business days to IUPUI IRB, DSMB, and NIH. Non-serious adverse events will be reported at time of continuing review to IUPUI IRB. In cases where there is any question regarding the level of adverse event or attributable cause, we will consult with the DSMB.

Non-serious adverse events are defined as: 1) outpatient surgical procedure, 2) sought advice from a physician or medical professional regarding a problem related to prescription medications, 3) experienced pain, fatigue, dizziness, or acute illness requiring no hospitalization related to prescription medication use. Serious adverse events are defined as: death, life threatening event, inpatient hospitalization, permanent disability.

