at home. However, it is not known about other potential harms such as stigma. On the other hand, early detection of ADRD is considered part of the standard of care and screening for ADRD is part of the Annual Wellness Visit covered by Medicare. Such early detection would lead to receive appropriate and valuable care both pharmacologically and non-pharmacologically. Such treatment would decrease the patient's disability resulting from unrecognized or unmanaged ADRD and enhance the patients' adherence of medical management of other health conditions. The research personnel will be trained to recognize and minimize any potential discomfort and patients may discontinue participation at any time. If a respondent becomes anxious or upset, the local principal investigator will be notified to intervene. Loss of confidentiality is also a risk in this type of data collection. Our data management and quality assurance technique has proven effective in past trials in maintaining confidentiality, and all study personnel have completed training in Human Subjects Research and HIPAA standards.

In addition, there may be the following possible risks due to blood draw:

- Pain while blood is being drawn
- Bruising of skin on the area after blood draw
- Bleeding after blood draw may occur
- There may be other risks associated with blood draw which may not be known

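### The validation study carries the study blood draws, requested MRI and investigator disclosure, but the plan specifies no scheduled or structured adverse-event capture for it beyond self-report

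*Combined protocol and SAP*

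**What the plan says.** **Scope.** The opening of section F says the data and safety monitoring plan is for the pragmatic trials and the clinical validation study.

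**Sources.** Possible Adverse Events opens with "Adverse events will be monitored on an ongoing basis by the study manager from three sources". Two items follow. The first is "Self-initiated phone, e-mail, or in-person report by the participant in the clinic validation study", with reports from the primary care team for the pragmatic trials. The second is "Quarterly review of acute care utilization in the pragmatic trials". No third item appears.

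**Review schedule.** Data Monitoring and Reporting has two tables. The one headed "Data Type: Clinical Validation Study" covers accrual and completion, protocol violations, out-of-range data, and a risk-benefit assessment at the end of the study. It has no adverse-event row. The pragmatic-trial table has one, "Adverse events, Unscheduled acute care utilization", marked both quarterly and annual. The summary reports of adverse events are described as being produced for each pragmatic trial.

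**Exposure.** Section D.7.a puts a blood draw of about 30 ml, and MRI where needed, in the validation assessment. Section E, Potential risks, adds that "there may be the following possible risks due to blood draw" and lists pain, bruising, bleeding and unknown risks; a separate paragraph covers MRI. Under Protection against risk, the principal investigators "will disclose the finding of new information about" the patient's health, directly to the patient.

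**Other statements on detection.** Safety Monitoring Definitions says "We will use the EHR system to monitor the following AEs", and names emergency visits without admission, confidentiality breaches and suicidal ideation not needing intervention. SAE/AE Response and Reporting Procedure says staff learn of events through scheduled reviews of record data.

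**The concern.** The plan's only scheduled adverse-event review is attached to the trials in which the study itself performs no procedure on patients. The study in which blood may be drawn, a scan requested and a new finding disclosed by the research team has self-report as its one listed source and no scheduled review.

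Self-report is a weak route in this setting. The study looks for undiagnosed cognitive impairment, so some of the people most affected by a disclosure may be among those least able to remember and volunteer a problem.

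At stake is the safety information behind the end-of-study risk-benefit assessment and the monitoring board's periodic view of risk against benefit. With no structured enquiry, an absence of reports could be read as an absence of harm. Potential risks itself says that harms such as stigma are not known and that blood draw may carry unknown risks.

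**Working it through.** There is no plan figure to reproduce and no arithmetic to apply. The check sets every statement on adverse-event capture beside the procedures of the validation study.

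**1. Which study carries the exposure?**
- Blood tests and MRI are part of the validation assessment (D.7.a). D.7.a has them requested when relevant to the diagnosis and missing from the record, so they are conditional.
- In the pragmatic trials, laboratory tests and imaging are ordered by providers and counted as outcomes (D.7.b). They are not study procedures.
- Investigator disclosure applies in practice to the validation study, because the pragmatic-trial data are de-identified and collected under a waiver (section E, Sources of material).

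**2. What could capture an event in a validation participant?**

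| Statement | Covers validation participants? | Scheduled? | Linked to adverse-event recording? |
|---|---|---|---|
| Self-report (Possible Adverse Events) | Yes, by name | No | Yes |
| Quarterly acute-care review (same section) | No, pragmatic trials | Yes | Yes |
| Review table for the validation study | Yes | No adverse-event row | No |
| Record monitoring (Safety Monitoring Definitions) | Not stated | Not stated | Yes, for the named events |
| Scheduled record reviews (SAE/AE Response and Reporting Procedure) | Not stated | The only schedule given is the pragmatic trials' | Yes |
| Investigator told if a respondent is upset (Potential risks) | Yes | No | Not stated; the purpose is to intervene |
| Continuous feedback from patients and practices (Protection against risk) | Yes | No timing given | Not stated; it concerns problems during data collection |

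No row combines clear coverage of validation participants, a schedule and a link to recording.

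**3. Would record review pick up the events in question?** The non-serious events named for record monitoring are emergency visits, confidentiality breaches and suicidal ideation. Bruising, distress in the scanner or ordinary distress after disclosure falls under none of these unless it leads to acute care. The Geriatric Depression Scale in D.7.a does not fill the gap. It is part of the assessment, which precedes the consensus diagnosis, so it cannot register a reaction to that diagnosis.

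**4. Would such an event count if reported?** Safety Monitoring Definitions has a broad definition that would cover a bruise. Possible Adverse Events defines non-serious events differently: outpatient surgery, seeking advice about a prescription-medication problem, and pain, fatigue, dizziness or acute illness tied to prescription medication. A blood-draw or disclosure event does not clearly qualify there.

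**5. How large is the effect?** This would need an event rate, a capture proportion for self-report and the number exposed to each procedure. The documents give none of them. They give only the 400 participants planned (D.3).

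**The case against.** The strongest reply is that capture does not rest on self-report alone. Record monitoring is described in general terms under a plan that covers all the studies, and identified record data are collected for validation participants. Staff are trained to recognise discomfort, the local investigator is told if a respondent is upset, MRI discomfort leads to a pause, and continuous feedback is planned. The monitoring board weighs risk against benefit for all three studies. The source list announces three items and shows two; whether the third was never written or was lost from the file cannot be settled from the text, so nothing exclusive can be read from that list.

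This stands against one tempting inference: that validation events are captured only if participants volunteer them, so that harms will be undercounted. The documents support neither the *only* nor the *will*. The reply does not show a scheduled or recorded enquiry that would find non-acute events after a procedure or a disclosure.

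The contrast with the pragmatic trials also needs care. Record review and clinic reports are the practical routes there, because patients are under a consent waiver. New diagnoses arise there too: Potential risks expects up to 13%. What sets the validation study apart is disclosure by the investigators.

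Finally, no adverse-event endpoint or analysis is planned in this study, and Aim 1 concerns AUC and accuracy. That is correct, and it limits the point to the quality of the safety data.

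**Conclusion.** The concern holds as a gap in ascertainment. For the study that in effect carries the study blood draws, study-requested MRI and investigator disclosure, the plan lists self-report as a source and schedules no adverse-event review. Its general statements on record review do not say whether or when they apply, and staff observation and feedback are not tied to recording. Non-acute events may be undercounted in the end-of-study risk-benefit assessment.

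No size can be attached. A reader might use the rule of three on all participants (3/400 = 0.75% as the upper 95% bound after no events) and widen it for incomplete reporting. The documents do not support this. The capture proportion would be invented, 400 is not a safe denominator for conditional tests, and a zero-event bound does not suit minor events, such as bruising, that the plan itself lists as possible.

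The conclusion assumes that no separate safety manual or case report form already contains such an enquiry; the documents mention none. It is a cheap improvement to the safety data and leaves the Aim 1 analysis untouched.

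**What to change.** 1. **Data Monitoring and Reporting:** add an adverse-event row to the validation table, marked for review at each occurrence and at the assessment.
2. **Enquiry:** add a short scripted adverse-event question, recorded in the existing REDCap database, at the end of the assessment or blood draw and again at the results contact described under Protection against risk. The second asking can also cover any MRI. State when and how the results contact takes place, since the plan gives neither.
3. **Possible Adverse Events:** list this enquiry as a source and state the third source that the section announces.
4. **Safety Monitoring Definitions and SAE/AE Response and Reporting Procedure:** say whether scheduled record review covers validation participants and, if so, at what interval.
5. **Definitions:** reconcile the largely medication-based list of non-serious events with Safety Monitoring Definitions, so that procedure-related and disclosure-related events count. Without this step the new form could collect events that the plan does not clearly recognise.

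**Cost:** one brief form, the time to ask it, and more minor events to record and report. No endpoint, sample size or analysis changes.
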